In all, 106 subjects were enrolled and treated with the FlowTriever System in FLARE, and 104 of these did not receive thrombolytics. Among these, 101 had evaluable CTPA studies suitable for the primary effectiveness endpoint. There were also 101 subjects that had 48-hour data suitable for the primary safety endpoint. The mean baseline RV/LV ratio was 1.5 ± 0.4 , and the mean 48-hour RV/LV ratio was 1.2 ± 0.3 . Three subjects had missing values for the primary effectiveness endpoint at the 48-hour visit resulting in 101 subjects with both a pre- and post-treatment RV/LV ratio for comparison. For these paired subjects, the mean change (reduction) in RV/LV ratio from pre- to post-treatment was 0.38 ± 0.3 , with a range from an increase of 0.4 to a decrease of 1.4. This mean change in RV/LV ratio was 0.38 (25.1%, $P < 0.0001$), indicating that the null hypothesis was rejected and the FlowTriever System met the performance goal.^b

For the primary safety endpoint, 4 subjects (3.8%) in the modified intention to treat population (all subjects with treatment attempted and no thrombolytics administered) experienced one or more MAEs. The composite endpoint of 3.8% was statistically lower than the performance goal of 25% ($P < 0.0001$), with an upper one-sided 95% confidence limit of 8.6%. None of the MAEs reported were device related.⁵⁷

In summary, the FLARE trial met its primary safety and effectiveness endpoints. This trial was the basis for the US FDA 510(k) clearance of the FlowTriever System for PE treatment in May 2018.

FLASH Study Design, Status, and Results

FLASH Study Design

The primary study objective of FLASH is to evaluate the safety and effectiveness of the next-generation FlowTriever System for use in the removal of emboli from the pulmonary arteries in the treatment of acute pulmonary embolism (PE). The use of the device is being assessed in a real-world population, with eligibility criteria that closely approximate its use in clinical practice.

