An interim analysis of outcomes out to 30 days on the first 230 subjects was presented at the 2021 Society for Interventional Radiology Annual Conference in March, 2021, with the abstract from this conference published in the Journal of Vascular and Interventional Radiology, as well as earlier conferences.⁵⁸⁻⁶⁰ These subjects (60.7 ± 13.9 years, 52.2% male) were enrolled across 17 sites, with 93.0% having intermediate-risk PE and 7.0% high-risk PE. The average baseline RV/LV ratio was 1.6 ± 0.5 and sPESI was 1.6 ± 1.1 . 96.3% of subjects had elevated biomarkers, and 69.7% of subjects had concomitant DVT. The primary endpoint of composite MAEs occurred in three (1.3%) subjects, all of which were non-ICH major bleeds, and no deaths occurred within 48 hours.

In-hospital outcomes demonstrated significant improvements across several acute parameters. Subjects experienced significant on-table hemodynamic improvements, including a 21.9% decrease in mean pulmonary artery pressure (32.0 mmHg to 25.0 mmHg, $P < 0.0001$) and a 20.1% decrease in heart rate (pre-procedural high of 113.2 bpm to 90.5 bpm immediately post-procedure, $P < 0.0001$). There was only one (0.4%) access site complication. The median post-procedure hospital length of stay was 3.0 [2.0 – 5.1] days and ICU length of stay was 0.0 [0.0 – 1.1] days.

30-day follow up data was available for 201 subjects in this analysis. In this population, there was one death (0.5% mortality), which was unrelated to the device, and there were ten hospital readmissions, one of which was related to the procedure. The average RV/LV ratio improved by 33.2% at a median follow up of 30 days ($P < 0.0001$) and subjects with confirmed baseline dyspnea had a significant improvement from baseline to 30 days (Modified Medical Research Council Dyspnea Scale, 3.0 ± 1.0 to 1.4 ± 1.3 , $P < 0.0001$).

These results of the FLASH all-comer registry demonstrate both safety and efficacy of the FlowTriever System, with a low all-cause mortality rate (0.0% at 48 hours, 0.5% at 30 days; no device-related deaths), along with significant and immediate hemodynamic improvements and continued improvements in RV/LV ratio and dyspnea out to 30 days.

FLAME Study Design and Status

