Taken together, these studies demonstrate that USAT is effective relative to AC, and like conventional CDT, the local delivery of smaller doses of thrombolytics compared to systemic administration likely provides greater patient safety. However, the question remained whether the ultrasound technology provided significant improvement over conventional CDT. To address this, Tafur, et al., performed a systematic review and meta-analysis of 23 studies and 700 subjects to summarize the evidence on safety and efficacy for conventional CDT versus USAT.⁴⁹ Of the included studies, 18 evaluated CDT only, 6 evaluated USAT only, and only one study evaluated and compared both treatments. The meta-analysis found no difference in the rate of bleeding complications between USAT and conventional catheter-directed thrombolysis, (total bleeding: 12% USAT vs. 10% CDT; major bleeding: 4% USAT vs. 10% CDT).⁴⁸ The review, however, documented a trend toward improved survival with USAT; 4% vs. 9% mortality in the USAT and conventional CDT subjects, respectively. However, the methods used to evaluate efficacy varied amongst studies, preventing a pooled comparative analysis. The authors conclude, however, that while the bleeding risk appeared to be lower with USAT treatments, the heterogeneity of the studies and lack of comparative data prevented them from reaching a definitive conclusion. They point out that the calculated mortality rates (4% for USAT and 9% for CDT) highlight the continued critical need for further study in this area.

Results from a more recent prospective, randomized control trial (SUNSET sPE) comparing USAT to CDT were recently published.⁴⁹ Eighty-one submassive PE patients from three clinical US centers were randomized 1:1 to either USAT or CDT and followed up out to 90 days. Primary efficacy outcomes of reductions in both pulmonary obstruction index and score were not different between the two groups. The reduction in RV/LV ratio from pre-procedure to 48 hours was statistically greater in the CDT group (USAT: 0.37 ± 0.34 ; CDT: 0.59 ± 0.42 ; $P=0.01$), and the overall mean hospital stay was shorter in the CDT arm as well (USAT: 4.1 ± 8.8 days; CDT: 2.4 ± 1.2 days; $P=0.03$). Two major and three minor bleeding events and one in-hospital death were recorded, all in the USAT group. The conclusion of this publication is that USAT may not confer a benefit over CDT.⁴⁹

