^f Imaging can be either echo or CT, but needs to be the same modality within each patient at Baseline and 24-hour visit

^g Note that the evaluation of endpoint considerations include All-cause mortality, ICH, Major bleeding, Clinical deterioration and/or escalation to a bailout therapy, and ICU admission and ICU length-of-stay. These are assessed at hospital discharge or 7 days after the index procedure, whichever is earlier. If a subject is still in the hospital and exits the study for any reason before the 30-day Visit, evaluation of primary endpoint components should be completed at the time of patient exit.

^h The Index Procedure begins when access for treatment is obtained. The Index Procedure is considered complete upon exit from the procedure room. The time of exit from the procedure room is the time reference used for the subsequent visit windows including the 24-hour visit.

BASELINE ASSESSMENTS

The baseline assessments must be done \leq 72 hours of Index Procedure including:

- Informed consent
- Inclusion/exclusion review
- Demographics
- Medical history, risk factors, and PE condition
- Anticoagulation regimen
- Clinical labs (Hemoglobin, Troponin)
- Cardiac imaging (Echo or CT)
 - Imaging can be either echo or CT, but needs to be the same modality within each patient at baseline and 24-hour visit.
- mMRC dyspnea score, Borg, and NYHA

ALLOCATION AND RANDOMIZATION

Upon the patient meeting baseline eligibility criteria and providing informed consent, a check against the list of absolute contraindications to thrombolytics is performed (see Figure 9: Patient Enrollment Flowchart). Subjects with one or more absolute contraindications to thrombolytics and whose initial treatment plan includes FlowTriever are allocated to the Contraindication Cohort. Subjects without any absolute contraindications (whether there are relative contraindications to thrombolytics or no contraindication to thrombolytics) are allocated to the RCT Cohort.

Study sites will receive the subject randomization assignment electronically in the electronic data capture (EDC) system upon completion of baseline information used to stratify randomization using the calculated VTE-BLEED score. Subjects will be randomized to and treated with (a) mechanical thrombectomy with FlowTriever or (b) catheter-directed thrombolysis per local practice standards.

INDEX PROCEDURE

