5.4.12. Change in RV/LV Ratio

Change in right-ventricular/left-ventricular (RV/LV) ratio from baseline to 24 hour visit, as measured by echocardiography or CT, will be analyzed as with the following null and alternative hypotheses:

$$H_0: \mu_{RF} \leq \mu_{RC} \text{ versus } H_A: \mu_{RF} > \mu_{RC}$$

where μ_{RF} represents the mean reduction in the RV/LV ratio treated from baseline to 24 hour visit in the FlowTriever System group, and μ_{RC} represents the mean reduction in the RV/LV ratio treated from baseline to 24 hour visit in the CDT group. The hypothesis will be tested using a Wilcoxon Rank Sum test.

5.4.13. mMRC Dyspnea Score at 24 Hour Visit

The mMRC Dyspnea score at 24 hour visit will be analyzed as with the following null and alternative hypotheses:

$$H_0: p_{mD24hF0} \leq p_{mD24hC0} \text{ and } p_{mD24hF1} \geq p_{mD24hC1} \text{ and } p_{mD24hF2} \geq p_{mD24hC2} \text{ and } p_{mD24hF3} \geq p_{mD24hC3} \text{ and } p_{mD24hF4} \geq p_{mD24hC4}$$

versus

$$H_A: p_{mD24hF0} > p_{mD24hC0} \text{ or } p_{mD24hF1} < p_{mD24hC1} \text{ or } p_{mD24hF2} < p_{mD24hC2} \text{ or } p_{mD24hF3} < p_{mD24hC3} \text{ or } p_{mD24hF4} < p_{mD24hC4}$$

PROPRIETARY AND CONFIDENTIAL

	PEERLESS Study: Statistical Analysis Plan	Version 5.0 March 22, 2024 Page 22 of 25
---	--	--

where $p_{mD24hFz}$ represents the proportion of subjects with mMRC Dyspnea Score equal to z at 24 hour visit in the FlowTriever System group, where $z = 0, 1, 2, 3$, and 4 ; and, $p_{mD24hCz}$ represents the proportion of subjects with mMRC Dyspnea Score equal to z at 24 hour visit in the CDT group, where $z = 0, 1, 2, 3$, and 4 . The hypothesis will be tested using a Fisher's exact test.

5.4.14. mMRC Dyspnea Score at 30 Day Visit

The mMRC Dyspnea score at 30 day visit will be analyzed as with the following null and alternative hypotheses:

$H_0: p_{mD30dF0} \leq p_{mD30dC0}$ and $p_{mD30dF1} \geq p_{mD30dC1}$ and $p_{mD30dF2} \geq p_{mD30dC2}$ and $p_{mD30dF3} \geq p_{mD30dC3}$ and $p_{mD30dF4} \geq p_{mD30dC4}$

versus

$H_A: p_{mD30dF0} > p_{mD30dC0}$ or $p_{mD30dF1} < p_{mD30dC1}$ or $p_{mD30dF2} < p_{mD30dC2}$ or $p_{mD30dF3} < p_{mD30dC3}$ or $p_{mD30dF4} < p_{mD30dC4}$

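### RV/LV change (SAP 5.4.12) is tested without baseline ratio, imaging modality or randomisation stratum; the test is not invalidated, but precision may be lost by an uncertain amount

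*SAP*

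**What the plan says.** SAP 5.4.12 states that "Change in right-ventricular/left-ventricular (RV/LV) ratio from baseline to 24 hour visit, as measured by echocardiography or CT, will be analyzed" with hypotheses on the mean reduction in each arm. The test is the rank sum test: "ratio treated from baseline to 24 hour visit in the CDT group. The hypothesis will be tested using a Wilcoxon Rank Sum test". Baseline enters only by subtraction. No between-arm estimate or interval is named for this endpoint.

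Protocol section 7, footnote f to the Schedule of Assessments, allows echo or CT but says that imaging "needs to be the same modality within each patient at Baseline and 24-hour visit". Modality is therefore constant within a patient and may differ between patients.

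Randomisation is 1:1, stratified by VTE-BLEED (Protocol section 6; SAP 2.1). The Finkelstein-Schoenfeld (F-S) test and the win ratio use all pairs regardless of stratum, and the bootstrap resamples by arm only (SAP 5.2 and 5.3). The other secondary tests are Fisher's exact or Wilcoxon tests without covariates (SAP 5.4). The only model in the SAP is the site poolability assessment (5.7).

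**The concern.** In large samples a change score is never more precise than least-squares adjustment for baseline. It is less precise whenever the slope of follow-up on baseline differs from 1, because subtraction fixes that slope at 1. Sicker patients at baseline usually have more room to improve, so a slope below 1 is plausible.

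The loss would fall on an endpoint that already faces a reduced alpha. SAP 5.6 divides one-sided 0.025 by an effective number of tests across the non-safety secondary endpoints. Counting both mMRC visits and both quality-of-life scores, there are up to seven of these.

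Adjustment would need no new data. Baseline imaging, modality and stratum are collected, and a complete-case change score (SAP section 4) already drops anyone without a baseline ratio.

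**Working it through.** **The plan's own figure.** There is none to reproduce for RV/LV. The SAP gives no SD, target difference or power for it. The 216 per arm belongs to the primary endpoint and is used here only as a working size, assuming paired imaging in every subject.

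**Inputs.** Protocol section 3, FLARE Study Results: "The mean baseline RV/LV ratio was 1.5 ± 0.4", a 48-hour SD of 0.3, and "the mean change (reduction) in RV/LV ratio from pre- to post-treatment was" 0.38 with SD 0.3. These are single-arm, CTPA, 48-hour figures printed to one decimal.

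**Variance ratio.**
- Correlation: r = (0.4² + 0.3² − 0.3²) / (2 × 0.4 × 0.3) = 0.16 / 0.24 = 0.667.
- Slope of follow-up on baseline: 0.667 × 0.3 / 0.4 = 0.50.
- ANCOVA variance over change-score variance: 0.3² × (1 − 0.667²) / 0.3² = 0.556.
- Residual SD: 0.300 for change, 0.3 × √0.556 = 0.224 for ANCOVA.

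**Detectable difference** (80% power, one-sided 0.025, 216 per arm) = (1.960 + 0.842) × SD × √(2/216), with √(2/216) = 0.0962.
- Change score: 2.802 × 0.300 × 0.0962 = 0.081. The Wilcoxon version under normality is √(π/3) times this, 0.083.
- ANCOVA: 2.802 × 0.224 × 0.0962 = 0.060.

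Each printed SD could be off by up to 0.05. The range must be computed from sets of SDs that can occur together:

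| SDs allowed to vary | Variance ratio | Detectable, change | Detectable, ANCOVA |
|---|---|---|---|
| None (0.4, 0.3, 0.3) | 0.56 | 0.081 | 0.060 |
| Baseline and follow-up; change held at 0.30 | 0.27–0.82 | 0.081 | 0.042–0.073 |
| All three | 0.19–0.87 | 0.067–0.094 | 0.029–0.082 |

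Both extremes of the last ratio range occur at a change SD of 0.25, so they should not be combined with 0.30.

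**Power for an assumed difference of 0.06, normal data, 216 per arm.**
- Wilcoxon: Φ(0.06/0.0289 × √(3/π) − 1.96) = Φ(0.07), about 53%.
- ANCOVA: Φ(0.06/0.0215 − 1.96) = Φ(0.83), about 80%.
- At the least favourable SDs (0.35, 0.35, 0.25; ratio 0.87): change score 70%, ANCOVA 76%.
- At 0.025/7 (z = 2.69), printed SDs: change score 27%, ANCOVA 54%.

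**Heavy tails.** Simulation with t-distributed data (5 and 3.5 degrees of freedom), difference 0.06:
- Printed SDs: ANCOVA leads the Wilcoxon test by about 17 and 8 points when both measurements share the heavy tail (a repeat run gave 16 and 7). It leads by about 20 and 13 when the tails are generated independently.
- Least favourable SDs, shared tail: Wilcoxon 78% against ANCOVA 75% (5 df), and 87% against 77% (3.5 df). The gain is gone or reversed.

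**Large difference.** The only randomised between-arm RV/LV difference in the documents comes from a comparison of two thrombolysis arms: "The reduction in RV/LV ratio from pre-procedure to 48 hours was statistically greater in the CDT group" (0.59 against 0.37, a difference of 0.22). With SD 0.30, the planned test has over 99.9% power at that size, so adjustment cannot add any.

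**Validity.** Under stratified 1:1 randomisation with an assumed prognostic stratum, the unstratified F-S test rejected in 1.9% of null trials at nominal 2.5% (stratified version 2.5%). Ignoring the stratum was conservative there. In null simulations the Wilcoxon test on change rejected in 2.1% to 2.8%.

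**The case against.** The strongest reply is that this is a preference. Change in RV/LV is the endpoint named in both documents, subtraction already uses baseline, and no error rate is harmed. The precision argument compares least-squares estimators, whereas the plan uses a rank test, which gains on ANCOVA when tails are long. FLARE hints at a long tail: its largest reduction was 1.4, or (1.4 − 0.38)/0.3 = 3.4 SD above the mean among 101 paired subjects. Under normality the chance of that is about 3%, or about 16% if the SD is really 0.35. FLARE also differs from this trial in having one arm, one modality and a 48-hour visit. Rounding limits are not plausibility limits: with equal SDs of 0.4 and a correlation of 0.9 the variance gain is only 5%.

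Most of this stands, and it limits the claim. It does not remove it. The stated hypothesis is about means, which ANCOVA estimates directly under randomisation. Every SD set consistent with the printed FLARE figures has a slope below 0.75. At the printed SDs ANCOVA stays ahead in both heavy-tailed simulations.

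A reader might infer that stratified randomisation obliges a stratified primary test. The documents do not support that. Protocol Table 1 presents VTE-BLEED as a score for bleeding risk on stable anticoagulation, nothing links it to ICU stay, and any gain would rest on assumed rates. A reader might also extend the point to mMRC. FLASH reports that "subjects with confirmed baseline dyspnea had a significant improvement from baseline to 30 days", but it gives no SD of change, so no correlation or gain can be derived.

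**Conclusion.** The point holds as an optional improvement in precision for one secondary endpoint. No stated test uses the stratum or a baseline covariate, and for RV/LV this probably costs precision. The indicative variance ratio is 0.56. It rests on rounded single-arm SDs at 48 hours and on normality. The benefit could be substantial for true differences near 0.06, negligible or negative with heavy tails and unfavourable SDs, and nil for a difference as large as 0.22, where only the confidence interval might narrow.

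Two stronger readings should be resisted. The omission does not make the tests invalid: it does not inflate type I error. Nor does this clear every test in the SAP. The multi-category Fisher tests for ICU stay and mMRC (5.4.7, 5.4.13, 5.4.14) are non-directional while their hypotheses are directional, which is a separate question not settled here.

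**What to change.** In SAP 5.4.12, pre-specify ANCOVA of the 24 h RV/LV ratio on treatment, baseline ratio, imaging modality and VTE-BLEED stratum, with robust standard errors. Report the adjusted mean difference with its confidence interval. Keep the Wilcoxon test on change, or a rank-based ANCOVA, as the sensitivity analysis for heavy tails.

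Fix this while the biostatistics team is still masked (SAP section 6). Because the trial is open-label and the SAP is at version 5.0, record the date and masking status of the change.

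The cost is SAP wording and programming, with no new data. The protocol names no test for the secondary endpoints, so it needs no amendment. The small downside is that ANCOVA is less robust to outliers than the rank test.

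Leave the primary F-S test as it is. A VTE-BLEED-stratified F-S analysis is optional and should carry no claimed gain. Do not adjust mMRC unless a model is named, for example proportional odds on treatment, baseline mMRC and stratum.

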5.4.15. Length of Post-Index-Procedure Hospital Stay

The length of post-index-procedure hospital stay (to a maximum of 30 days) will be analyzed as with the following null and alternative hypotheses:

$H_0: \mu_{PHSF} \geq \mu_{PHSC}$ versus $H_A: \mu_{PHSF} < \mu_{PHSC}$

where μ_{PHSF} represents the mean length of post-index-procedure hospital stay in the FlowTriever System group, and μ_{PHSC} represents the mean length of post-index-procedure hospital stay in the CDT group. The hypothesis will be tested using a Wilcoxon Rank Sum test.

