5.4.16. Disease-Specific Quality of Life at 30 Day Visit – PEmb-QoL

The PEmb-QoL at 30 days visit will be analyzed as with the following null and alternative hypotheses:

$H_0: \mu_{PQF} \geq \mu_{PQC}$ versus $H_A: \mu_{PQF} < \mu_{PQC}$

where μ_{PQF} represents the mean PEmb-QoL score at 30 day visit in the FlowTriever System group, and μ_{PQC} represents the mean PEmb-QoL score at 30 day visit in the CDT group. The hypothesis will be tested using a Wilcoxon Rank Sum test.

PROPRIETARY AND CONFIDENTIAL

The information contained in this document is the sole property of Inari Medical

	PEERLESS Study: Statistical Analysis Plan	Version 5.0 March 22, 2024 Page 23 of 25
---	--	--

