5.4.17. General Health-Related Quality of Life at 30 Day Visit – EQ-5D-5L

The EQ-5D-5L at 30 days visit will be analyzed as with the following null and alternative hypotheses:

$$H_0: \mu_{EQF} \leq \mu_{EQC} \text{ versus } H_A: \mu_{EQF} > \mu_{EQC}$$

where μ_{EQF} represents the mean EQ-5D-5L score at 30 day visit in the FlowTriever System group, and μ_{EQC} represents the mean EQ-5D-5L score at 30 day visit in the CDT group. The hypothesis will be tested using a Wilcoxon Rank Sum test.

The secondary endpoints listed in this section will be assessed for patients in ITT and PP populations with descriptive statistics and hypothesis testing. Continuous variables will report any combination of mean, SD, median, Q1, Q3, IQR, minimum and maximum, while the categorical variables will report frequency count and percentages (%).

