- mMRC Dyspnea score at 24 hour visit and 30 day visit
- Length of post-index-procedure hospital stay (to a maximum of 30 days)
- Disease-specific and general health-related quality of life at the 30 day visit (PEmb-QoL and EQ-5D-5L)

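### SAP 5.4.12 and 5.4.15–5.4.17 state hypotheses about means but test them with a rank-sum test, which does not control the error rate for means when the two arms differ in shape

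*SAP*

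**What the plan says.** SAP 5.4.15 gives a one-sided hypothesis on stay capped at 30 days: H0, FlowTriever mean ≥ CDT mean; H_A, FlowTriever mean < CDT mean. The FlowTriever symbol "represents the mean length of post-index-procedure hospital stay in the FlowTriever System group". The CDT symbol and the test follow directly: it "represents the mean length of post-index-procedure hospital stay in the CDT group. The hypothesis will be tested using a Wilcoxon Rank Sum test".

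The quality-of-life sections are built the same way. In 5.4.16 the CDT symbol "represents the mean PEmb-QoL score at 30 day visit in the CDT group. The hypothesis will be tested using a Wilcoxon Rank Sum test"; in 5.4.17 it "represents the mean EQ-5D-5L score at 30 day visit in the CDT group. The hypothesis will be tested using a Wilcoxon Rank Sum test". Section 5.4.12 has the same pairing for mean reduction in RV/LV ratio from baseline to the 24-hour visit.

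Neither document assumes a shift or a common shape, words these hypotheses in rank terms, or adds a test or interval for the difference in means. SAP 5.6 puts all four endpoints in the non-safety family, controlled at one-sided 0.025 with a Bonferroni-type divisor whose value is not given. The closing paragraph of 5.4.17 leaves open which descriptive statistics are shown for continuous variables, so a reported mean is not guaranteed.

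**The concern.** The rank-sum test takes its reference distribution from the hypothesis that the two arms have identical distributions. Its power is against P(FlowTriever stay shorter) + 0.5 P(tie) differing from 1/2. That quantity and the difference in means can part company when the arms' shapes differ: a treatment can shorten the typical stay and lengthen the tail, or the reverse.

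Under the SAP's own H_A, a significant result would be read as a shorter mean stay. Total bed-days and cost follow the mean, and the protocol's study justification (section 8) speaks of ICU bed use and cost. With unequal shapes that reading is not protected at the stated error rate. A true difference in means carried by a few very long stays could also be missed.

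**Working it through.** The plan gives no effect size, power or sample size for hospital stay, so there is no figure of its own to reproduce. The check is of the error rate under the stated mean hypothesis.

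**Inputs**
- FlowTriever post-procedure stay, FLASH interim results (Protocol section 3): median 3.0 days, quartiles 2.0 and 5.1.
- Size: 550 randomized 1:1, so 275 per arm (SAP 5.1).
- Cap: 30 days (SAP 5.4.15).
- Level: one-sided 0.025. SAP 5.6 lists seven non-safety tests (ICU, RV/LV, mMRC twice, stay, PEmb-QoL, EQ-5D-5L), so the divisor may lie between 1 and 7; 0.025/7 = 0.00357.
- Assumptions: log-normal stays, and the CDT spread.

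**FlowTriever arm.** Log-SD = ln(5.1/2.0)/(2 × 0.6745) = 0.694. Mean = 3.0 × exp(0.694²/2) = 3.82, or 3.81 after the cap.

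**CDT arm.** Give it exactly the same capped mean and a narrower log-SD; the median then has to rise. Rejection means declaring FlowTriever shorter although the means are equal.

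| CDT log-SD (assumed) | CDT median, days | Wilcoxon at 0.025 | Wilcoxon at 0.00357 |
|---|---|---|---|
| 0.694 (same shape) | 3.00 | about 3% | about 0.3–0.4% |
| 0.65 | 3.09 | 6–7% | about 1% |
| 0.60 | 3.19 | 18–19% | 5% |
| 0.55 | 3.28 | 36–38% | 14% |
| 0.50 | 3.37 | 58% | 30–31% |
| 0.40 | 3.52 | 89–90% | 69–70% |

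A Welch test on the same data stays at about 3% at the 0.025 level.

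**Hand check, log-SD 0.50.** P(FlowTriever shorter) = Φ[ln(3.37/3.00)/√(0.694² + 0.50²)] = Φ(0.116/0.855) = 0.554. The null standard error of this probability is √[551/(12 × 275²)] = 0.0246. Rejection probability ≈ Φ(0.054/0.0246 − 1.96) = Φ(0.2), about 58–59%, as simulated.

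**A control arm built from the protocol's own CDT-type stays.** Protocol section 3 says of a randomized comparison of ultrasound-assisted with conventional CDT that "the overall mean hospital stay was shorter in the CDT arm as well (USAT: 4.1" ± 8.8 days, against 2.4 ± 1.2 with conventional CDT. Both are permitted control treatments in this trial. A 50/50 pool has SD √[0.5 × (8.8² + 1.2²) + 0.25 × 1.7²] = 6.3 days, wider than FLASH (log-normal SD 3.0). Scaled to the FLASH capped mean, Wilcoxon declares FlowTriever shorter in 0.9%, 0.0% and 0.0% of trials with 25%, 50% and 75% ultrasound-assisted patients. If the control arm had the ultrasound-assisted spread throughout, the ranks would point to FlowTriever being longer in at least 99.9% of trials, again at equal means.

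**When nothing goes wrong.** If one arm is stochastically shorter, its mean is shorter and its rank probability is on the same side of 1/2. Multiplying FLASH stays by 1.15 for FlowTriever gives 0.0% false claims. Multiplying by 0.85 gives power of 77% for Wilcoxon and 68% for Welch.

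**The case against.** The strongest defense is that Wilcoxon is a sensible choice for skewed stays and that only the wording is loose. Much of this stands. Skew alone does no harm, any stochastic ordering keeps the two conclusions aligned, and Wilcoxon can be the more powerful test, as the scaling example shows. These are secondary endpoints under a multiplicity correction, and the recommended change leaves the p-value as it is. What does not stand is the step from a significant rank test to a statement about means, which is the step the SAP's hypotheses take.

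A reader might go further and infer that the protocol's own figures show the test would falsely favor FlowTriever. They do not:
- Setting 4.1 ± 8.8 and 2.4 ± 1.2 as the two arms does give striking results: Wilcoxon calls the longer-mean arm shorter in 68–69% of trials, or with the arms exchanged has 0% power against 99% for Welch. But both inputs are control-type treatments, so this says nothing about FlowTriever against CDT.
- The log-normal fit to those figures is itself doubtful. It puts the ultrasound-assisted median (1.73) below the conventional one (2.15). The source reports P = 0.03 with conventional CDT shorter. At about 40 per arm, the printed means and SDs give t = 1.7/√(8.8²/40 + 1.2²/40) = 1.21, P about 0.23. The 0.03 therefore probably came from a rank-type test that agreed with the means (an inference).
- The single-center retrospective comparison (FlowTriever 2.1 ± 1.2, routine care 6.1 ± 8.6) shows no conflict: log-normals matched to it give 100% rejection with both tests.
- The randomized and retrospective figures describe hospital stay, not capped post-procedure stay.

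**Conclusion.** The mismatch is in the SAP text and should be corrected in 5.4.12 and 5.4.15–5.4.17. For stay, with equal means and FlowTriever at the FLASH spread, the chance of wrongly declaring a shorter mean stay runs from 0–1% (pooled control figures) through about 3% (equal shapes) to about 6–90% (CDT log-SD 0.65 down to 0.40). These rates rest on log-normal shapes, and the CDT log-SDs are assumed; neither document gives one. The size and direction in this trial are unknown, so the numbers show what the test permits, not what it will do. For the other three endpoints no comparable range was worked out. The weight is minor: the primary analysis and the required sample size do not depend on it.

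**What to change.** - Keep the Wilcoxon test. In 5.4.12 and 5.4.15–5.4.17 restate the hypotheses as H0: P(FlowTriever better) + 0.5 P(tie) ≤ 1/2 against H_A: > 1/2. Better means shorter stay, lower PEmb-QoL, higher EQ-5D-5L and larger RV/LV reduction, as the present alternatives imply.
- Report that probability with a 95% CI that allows unequal spread (Brunner-Munzel type).
- Always report the difference in means, with stay capped at 30 days, and a Welch or bootstrap 95% CI. Base any statement about mean days, mean score or mean RV/LV reduction on that interval only.

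The cost is SAP wording and two estimates per endpoint from data already collected, with no loss of power. A significant Wilcoxon result alone would no longer support a claim about means, and its p-value and the unequal-spread interval may occasionally disagree. Replacing Wilcoxon with Welch is not needed; it is a trade-off that can lose power when the bulk of the distribution shifts.
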